7.3 Duration of Participation

Describe how long subjects will be involved in this research study. Include the number of sessions and the duration of each session - consider the total number of minutes, hours, days, months, years, etc.

Participation in this study will take about 6 months. It is anticipated that Visit 1 will last approximately 45 minutes, 15 minutes for the questions and 30 minutes to instruct in the use of the devices. This may be divided among consecutive visits based on standard care.

7.4 Test Article(s) (Study Drug(s) and/or Study Device(s))**7.4.1 Description**

Provide a brief description of all test articles (drugs (including any foods and dietary supplements), devices and/or biologics used in the research including the purpose of their use and their approval status with the Food and Drug Administration (FDA). Include information about the form of the drug product (e.g., tablets, capsules, liquid).

N/A

7.4.2 Treatment Regimen

Describe dose, route of administration and treatment duration. Include information about dose adjustments.

N/A

7.4.3 Method for Assigning Subject to Treatment Groups

Describe the randomization process and how the associated treatment assignment will be made.

N/A

7.4.4 Subject Compliance Monitoring

Insert the procedures for monitoring subject compliance.

N/A

7.4.5 Blinding of the Test Article

Describe how the test article is blinded.

N/A

7.4.6 Receiving, Storage, Dispensing and Return**7.4.6.1 Receipt of Test Article**

Describe how the test article will be obtained and from what source. Describe how the study test article will be

packaged along with amounts (e.g., number of tablets/capsules or volume of liquid) and labeling. If drug kits are used, describe all the contents of the kit and associated labeling.

N/A

7.4.6.2

Storage

Describe the plans to store, handle the test article so they will be used only on subjects and only by authorized investigators. Describe storage temperature requirements and how temperature will be monitored and recorded.

N/A

7.4.6.3

Preparation and Dispensing

Describe how the test article will be assigned to each subject and dispensed. Describe the steps necessary to prepare the test article. Include where the test article preparation will be done and by whom. Fully describe how the study treatment is to be administered and by whom.

N/A

7.4.6.4

Return or Destruction of the Test Article

Describe the procedures for final reconciliation of the test article supply at the end of the study and whether the test article is to be shipped back to a source or destroyed on site.

N/A

7.4.6.5

Prior and Concomitant Therapy

Describe what prior and/or concomitant medical therapy will be collected. Describe which concomitant medicines/therapies are permitted during the study. Describe which concomitant medicines are not permitted during the study.

N/A

****Site Congruency: Is the information provided in the above section (Study Design and Procedures) consistent across all relying sites in this research?**

Yes

No - Identify the sites that have dissimilar procedures: *[This field should solely identify the site. Dissimilar procedures across sites should be identified in the SITE workspace via HRP-XXX – R2S Site Plan]*

8.0 Number of Subject and Statistical Plan

8.1 Number of Subjects

Indicate the maximum number of subjects to be accrued/enrolled. Distinguish between the number of subjects who are expected to be enrolled and screened, and the number of subjects needed to complete the research procedures if applicable (i.e., numbers of subjects excluding screen failures.)

We anticipate enrolling 20 pregnant women for this pilot study.

8.2 Sample size determination

If applicable, provide a justification of the sample size outlined in section 8.1 to include reflections on, or calculations of, the power of the study.

Because this is a pilot study, no formal sample size calculations were completed.

8.3 Statistical methods

Describe the statistical methods (or non-statistical methods of analysis) that will be employed.

Descriptive statistics for surveys as well as feasibility (e.g., recruitment and retention, fidelity, data collection methods) and acceptability (e.g., satisfaction) will be calculated.

9.0 Data and Safety Monitoring Plan

This section is required when research involves more than Minimal Risk to subjects as defined in “HRP-001 SOP- Definitions.”

Minimal Risk is defined as the probability and magnitude of harm or discomfort anticipated in the research that are not greater in and of themselves than those ordinarily encountered in daily life or during the performance of routine physical or psychological examinations or tests. For research involving prisoners, Minimal Risk is the probability and magnitude of physical or psychological harm that is normally encountered in the daily lives, or in the routine medical, dental, or psychological examination of healthy persons.

Please complete the sections below if the research involves more than minimal risk to subjects, otherwise indicate each section as not applicable.

[Do not type here]

9.1 Periodic evaluation of data

Describe the plan to periodically evaluate the data collected regarding both harms and benefits to determine whether subjects remain safe.

N/A

9.2 Data that are reviewed

Describe the data that are reviewed, including safety data, untoward events, and efficacy data.

N/A

9.3 Method of collection of safety information

Describe the method by which the safety information will be collected (e.g., with case report forms, at study visits, by telephone calls and with subjects).

N/A

9.4 Frequency of data collection

Describe the frequency of data collection, including when safety data collection starts.

N/A

9.5 Individuals reviewing the data

Identify the individuals who will review the data. The plan might include establishing a data and safety monitoring committee and a plan for reporting data monitoring committee findings to the IRB and the sponsor.

N/A

9.6 Frequency of review of cumulative data

Describe the frequency or periodicity of review of cumulative data.

N/A

9.7 Statistical tests

Describe the statistical tests for analyzing the safety data to determine whether harms are occurring.

N/A

9.8 Suspension of research

Describe any conditions that trigger an immediate suspension of research.

N/A

10.0 Risks

List the reasonably foreseeable risks, discomforts, hazards, or inconveniences to the subjects related to the subjects' participation in the research. Include as may be useful for the IRB's consideration, a description of the probability, magnitude, duration and reversibility of the risks. Consider all types of risk including physical, psychological, social, legal, and economic risks. Note: Loss of confidentiality is a potential risk when conducting human subject research.

- If applicable, indicate which procedures may have risks to the subjects that are currently unforeseeable.
- If applicable, indicate which procedures may have risks to an embryo or fetus should the subject be or become pregnant.
- If applicable, describe risks to others who are not subjects.

This study involves no major health risks to participants, and we implement procedures to minimize any potential risks. There is a slight risk of musculoskeletal joint pain, strains, aches and injuries associated with moderate-intensity physical activity. Physical activity is a component of the proposed intervention. NFP home visitors will educate participants about recommendations regarding physical activity in pregnancy based on current guidelines such as those from the American College of Obstetrics and Gynecology. We will minimize the risk of injury by providing proper exercise technique instruction, including the importance of warm-up and cool-down exercises and proper stretching techniques. We will minimize the risk of injury during pregnancy by emphasizing appropriate precautions (e.g., avoidance of activities with potential for trauma such as contact sports and skiing).

As with all studies, there is some risk to the participant's confidentiality. The study follows procedures to minimize the potential risk to participant confidentiality. To protect participant's confidentiality, we store study information using only a study identification number and no other information that could identify an individual. All information is stored in secure computers and moved using secure data transfer methods. We destroy all study records at the end of the study. Any information from this study we present in reports or publications will not identify any individual.

11.0 Potential Benefits to Subjects and Others

11.1 Potential Benefits to Subjects

Describe the potential benefits that individual subjects may experience from taking part in the research. If there is no direct benefit to subjects, indicate as such. Compensation is not considered a benefit. Compensation should be addressed in section 14.0.

There is no guarantee that participants will benefit from this pilot study. The possible benefits include improved physical activity patterns, reduced nicotine use, earlier detection of hypertension, and improved sleep which could lead to improved pregnancy outcomes like easier labor and fewer complications. The lifestyle changes, if maintained, have the possibility of leading to long-term reduction in obesity and its associated risks, such as hypertension and diabetes. Other possible benefits include improved recognition of hypertensive disorders during and after pregnancy, as well as assistance with smoking cessation for those who smoke.

11.2 Potential Benefits to Others

Include benefits to society or others.

The results of the research will help scientists to better understand the feasibility and acceptability of delivering enhanced intervention content during NFP program home visits. Understanding these factors will help scientists designed a large scale, multi-site trial designed to improve CVH for women and infants.

12.0 Sharing Results with Subjects

Describe whether results (study results or individual subject results, such as results of investigational diagnostic tests, genetic tests, or incidental findings) will be shared with subjects or others (e.g., the subject's primary care physicians) and if so, describe how information will be shared.

No results will be shared with participants.

13.0 Subject Payment and/or Travel Reimbursements

Describe the amount, type (cash, check, gift card, other) and timing of any subject payment or travel reimbursement. If there is **no** subject payment or travel reimbursement, indicate as not applicable.

Extra or Course Credit: Describe the amount of credit **and** the available alternatives. Alternatives should be equal in time and effort to the amount of course or extra credit offered. It is not acceptable to indicate that the amount of credit is to be determined or at the discretion of the instructor of the course.

Approved Subject Pool: Indicate which approved subject pool will be used; include in response below that course credit will be given and alternatives will be offered as per the approved subject pool procedures.

Participants are eligible to receive up to \$300. Participants will receive \$100.00 after completing the first study visit and baseline survey. Upon completing the second study visit, participants will receive \$100.00. Upon completing the last study visit and follow-up survey, participants will receive \$100.00. Participants will also get to keep the Fitbit and Fitbit Scale they have used during the study.

****Site Congruency: Is the information provided in the above section (Subject Payment and/or Travel Reimbursements) consistent across all relying sites in this research?**

Yes

No - Identify the sites that have dissimilar procedures: *[This field should solely identify the site. Dissimilar procedures across sites should be identified in the SITE workspace via HRP-XXX – R2S Site Plan]*

14.0 Economic Burden to Subjects

14.1 Costs

Describe any costs that subjects may be responsible for because of participation in the research.

Participants will not incur any costs because of participation in this research.

14.2 Compensation for research-related injury

If the research involves more than Minimal Risk to subjects, describe the available compensation in the event of research related injury.

If there is no sponsor agreement that addresses compensation for medical care for research subjects with a research-related injury, include the following text as written - DO NOT ALTER OR DELETE:

It is the policy of the institution to provide neither financial compensation nor free medical treatment for research-related injury. In the event of injury resulting from this research, medical treatment is available but will be provided at the usual charge. Costs for the treatment of research-related injuries will be charged to subjects or their insurance carriers.

For sponsored research studies with a research agreement with the sponsor that addresses compensation for medical care for research-related injuries, include the following text as written - DO NOT ALTER OR DELETE:

It is the policy of the institution to provide neither financial compensation nor free medical treatment for research-related injury. In the event of injury resulting from this research, medical treatment is available but will be provided at the usual charge. Such charges may be paid by the study sponsor as outlined in the research agreement and explained in the consent form.

N/A

15.0 Resources Available

15.1 Facilities and locations

Identify and describe the facilities, sites and locations where recruitment and study procedures will be performed by the PSU study team.

If research will be conducted outside the United States by the PSU study team, describe site-specific regulations or customs affecting the research, and describe the process for obtaining local ethical review. Also, describe the principal investigator's experience conducting research at these locations and familiarity with local culture.

Recruitment will most likely take place in the home of the participants, where study procedures will also all occur. Occasionally, those participating in NFP meet at other mutually agreed upon locations.

15.2 Feasibility of recruiting the required number of subjects

Indicate the number of potential subjects to which the PSU study team has access. Indicate the percentage of those potential subjects needed for recruitment.

Given the small sample size for this pilot study, it is feasible to recruit the number of subjects needed. Our two NFP agency partners enroll several hundred pregnant women into their programs annually. The Center for Childhood Obesity Research (CCOR) has previous experience recruiting pregnant women and women who have recently delivered and has long standing working relationship with Geisinger and UPMC offices across the state.

15.3 PI Time devoted to conducting the research

Describe how the PSU PI will ensure that a sufficient amount of time will be devoted to conducting and completing the research. Please consider outside responsibilities as well as other on-going research for which the PSU PI is responsible.

The PI's will be responsible for overseeing all aspects of the study.

15.4 Availability of medical or psychological resources

Describe the availability of medical or psychological resources that subjects might need as a result of their participation in the study, if applicable.

N/A

15.5 Process for informing Study Team

Describe the training plans to ensure members of the PSU research team are informed about the protocol and their duties, if applicable.

The PI will provide training to all members of the study team related to recruitment and other aspects of this study. The research team will work collaboratively with the NFP agencies and their home visitors with a minimum of twice monthly meetings to discuss changes or issues.

16.0 Other Approvals

16.1 Other Approvals from External Entities

Describe any approvals that will be obtained prior to commencing the research (e.g., from community leaders, schools, research locations where research is to be conducted by the Penn State investigator, funding agencies, etc.).

N/A

16.2 Internal PSU Committee Approvals

Check all that apply:

- Anatomic Pathology – **Penn State Health only** – Research involves the collection of tissues or use of pathologic specimens. Upload a copy of “HRP-902 - Human Tissue For Research Form” in CATS IRB.
- Animal Care and Use – **All campuses** – Human research involves animals and humans or the use of human tissues in animals
- Biosafety – **All campuses** – Research involves biohazardous materials (human biological specimens in a PSU research lab, biological toxins, carcinogens, infectious agents, recombinant viruses or DNA or gene therapy).
- Clinical Laboratories – **Penn State Health only** – Collection, processing and/or storage of extra tubes of body fluid specimens for research purposes by the Clinical Laboratories; and/or use of body fluids that had been collected for clinical purposes but are no longer needed for clinical use.
- Clinical Research Center (CRC) Advisory Committee – **University Park** – Research involves the use of CRC services in any way.
- Conflict of Interest Review – **All campuses** – Research has one or more of study team members indicated as having a financial interest.
- Radiation Safety – **Penn State Health only** – Research involves research-related radiation procedures. All research involving radiation procedures (standard of care and/or research-related) must upload a copy of “HRP-903 - Radiation Review Form” in CATS IRB.
- IND/IDE Audit – **All campuses** – Research in which the PSU researcher holds the IND or IDE or intends to hold the IND or IDE.
- Scientific Review – **Penn State Health only** – All investigator-written research studies requiring review by the convened IRB must provide documentation of scientific review with the IRB

submission. The scientific review requirement may be fulfilled by one of the following: (1) external peer-review process; (2) department/institute scientific review committee; or (3) scientific review by the Clinical Research Center Advisory committee. NOTE: Review by the Penn State Health Cancer Institute (PSCI) Protocol Review Committee or the PSCI Disease Team is required if the study involves cancer prevention studies or cancer patients, records and/or tissues. For more information about this requirement see the IRB website.

St. Joseph Administrative Review – **Penn State Health only** – Penn State Health Research that will be conducted at St. Joseph Medical Center or St. Joseph Community Medical Groups.

17.0 Requests to Serve (R2S) Study Management

This section should describe the plan to ensure consistency and communication across all sites in this sIRB project.

[Do not type here]

17.2 Communication Plans

Describe the plan for regular communication between the PSU study team and the other sites to ensure that all sites have the most current version of the protocol, consent document, etc. Describe the process to ensure all modifications have been communicated to sites. Describe the process for communication of problems with the research, interim results and closure of the study.

PSU, Geisinger and UPMC team members have regularly scheduled meetings to discuss the protocol, consent document, and pilot study progress. All modifications as well as problems with the research, results, and closure of the study will be discussed during these meetings. Site investigators will have access to a secure, electronic data storage site that includes study protocols and procedures as well as minutes from regularly scheduled meetings.

17.3 Data Submission and Security Plan

Describe the process and schedule for data submission and provide the data security plan for data collected from other sites. Describe the process to ensure all engaged participating sites will safeguard data as required by local information security policies.

Most of the data for this pilot study will be collected electronically via REDCap, a secure web-based platform. CCOR will be responsible for all storage and management of electronic data. Any paper records (e.g., consent forms) will be stored in a locked cabinet in a locked office at the Center for Childhood Obesity Research at Penn State.

17.4 Subject Enrollment

Describe the procedures for coordination of subject enrollment and randomization for the overall project.

Potential participants will be recruited through established partnerships with Geisinger and UPMC Nurse Family Partnership agencies. After potential participants are identified by visiting nurses and/or their supervisors, visiting nurses will share information about the pilot study verbally and through a written summary handout prepared by the study team. Potential participants will be recruited in their homes during regularly scheduled home visits with their visiting nurse. Once recruited, visiting nurses will inform the study team at the Center for Childhood Obesity Research at Penn State. This is a pilot study to determine feasibility and acceptability and no randomization will occur.

17.5 Reporting of Adverse Events and New Information

Describe how adverse events and other information will be reported from the relying sites to the PSU study team. Provide the timeframe for this reporting.

We do not anticipate any research-related adverse events given the content of the behavioral intervention. NFP community-based nurses will report clinical concerns to the infant's primary care provider as is their usual practice. Should there be an emergency where the primary care provider is not available or concerns related to the specific intervention material arise, the NFP nurses will contact the study team including the PIs within 24 hours.

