18.2 Recording of Adverse Events

Address the frequency and process for eliciting adverse event information from research subject, e.g., “Research subjects will be routinely questioned about adverse events at study visits.”

In the response, incorporate the following as written:

All adverse events (serious or non-serious) and abnormal test findings observed or reported to study team believed to be associated with the study drug(s) or device(s) will be followed until the event (or its sequelae) or the abnormal test finding resolves or stabilizes at a level acceptable to the investigator.

An abnormal test finding will be classified as an adverse event if one or more of the following criteria are met:

- The test finding is accompanied by clinical symptoms
- The test finding necessitates additional diagnostic evaluation(s) or medical/surgical intervention; including significant additional concomitant drug treatment or other therapy

NOTE: Simply repeating a test finding, in the absence of any of the other listed criteria, does not constitute an adverse event.

- The test finding leads to a change in study drug dosing or discontinuation of subject participation in the clinical research study
- The test finding is considered an adverse event by the investigator.

Adverse events will be reported to the project coordinator on a monthly basis. Serious adverse events will be reported within 24 hours following IRB and NIH guidelines. Monthly research meetings will be the regularly scheduled time to convey new information about the study. More urgent information will be transmitted by email or phone.

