18.3 Causality and Severity Assessments

By submitting this study for review, you agree to the following statement – DO NOT ALTER OR DELETE:

The investigator will promptly review documented adverse events and abnormal test findings to determine 1) if the abnormal test finding should be classified as an adverse event; 2) if there is a reasonable possibility that the adverse event was caused by the study drug(s) or device(s); and 3) if the adverse event meets the criteria for a serious adverse event.

If the investigator's final determination of causality is "unknown and of questionable relationship to the study drug(s) or device(s)", the adverse event will be classified as associated with the use of the study drug(s) or device(s) for reporting purposes. If the investigator's final determination of causality is "unknown but not related to the study drug(s) or device(s)", this determination and the rationale for the determination will be documented in the respective subject's case history.

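### Section 17.5 sends nurses' clinical concerns to the infant's provider in a study of mothers, and does not repeat the 24-hour SAE rule of section 18.2

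*Combined protocol and SAP*

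**What the plan says.** Section 17.5 answers the template prompt "Describe how adverse events and other information will be reported from the relying sites to the PSU study team". After saying that no research-related events are expected, it states "NFP community-based nurses will report clinical concerns to the infant", and the sentence goes on to name that infant's primary care provider and to call this usual practice. It then gives two situations for faster contact with the team. One is an emergency in which the primary care provider cannot be reached. The other is worded "concerns related to the specific intervention material arise, the NFP nurses will contact the study team including the PIs within 24 hours".

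Section 18.2 covers recording of adverse events. It says "Adverse events will be reported to the project coordinator on a monthly basis", then "Serious adverse events will be reported within 24 hours following IRB and NIH guidelines", and, after a sentence on monthly meetings, "More urgent information will be transmitted by email or phone". Section 18.3 adds "The investigator will promptly review documented adverse events and abnormal test findings" to judge causality and seriousness.

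The participants are nulliparous pregnant women (3.1), 20 of them (8.1). The note before Table 1 in 7.2 says that the study-specific parameters are on mothers only. Section 5.2.1 says the NFP nurses will be added as study personnel.

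**The concern.** Section 17.5 is the text a site nurse would consult when something goes wrong with a participant. Followed literally, it points her to a clinician who does not look after the participant and who, during pregnancy, has no patient yet. A reporting rule should name the right recipient without relying on the nurse to correct it.

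The second issue is smaller. The nurse-specific 24-hour instruction in 17.5 is tied to two situations and does not mention SAEs as such, while 18.2 sets a 24-hour limit for SAEs with neither condition. A nurse who reads only the site-facing section would not find the general rule there. The investigator's review under 18.3 can start only once an event has reached the team, so the site-facing text should carry the same rule.

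**Working it through.** No figure in the plan bears on this point, so the check is a comparison of texts, with one piece of arithmetic for scale.

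**1. Who receives a clinical concern?**
- 17.5: one provider is identified, the infant's. No obstetric provider and no primary care provider of the mother is named. The following sentence says only the primary care provider, which most naturally refers back to the infant's.
- 7.2, blood pressure: the nurse reviews the log at each visit and refers for high readings. In pregnancy and the puerperium, a repeated reading above 140/90 prompts the woman to contact her obstetric provider. Later, a reading above 150/100 triggers a similar alert directed to her primary care provider. This is a maternal route, with the right recipients, for one kind of finding.
- 7.2, nicotine: the woman's own provider appears, but only to approve nicotine replacement or medication through the Quitline. This is not a route for a clinical concern.
- 10.0: "There is a slight risk of musculoskeletal joint pain, strains, aches and injuries associated with moderate-intensity physical activity". No maternal provider is named for such an injury.

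Maternal concerns other than blood pressure therefore have no maternal recipient stated in the plan, and the recipient that 17.5 does state is the wrong one.

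**2. How long does the named recipient not exist?**
Inputs: recruitment is before 28 weeks' gestation (4.2.3), and participation lasts about 6 months (7.3), or about 26 weeks. The documents give no expected gestation at birth, so I assume 37 to 40 weeks.
- Enrolled at the 28-week limit: 37 − 28 = 9 and 40 − 28 = 12, so about 9 to 12 weeks of study time before birth.
- Enrolled at 12 weeks (an assumed first-trimester entry): 37 − 12 = 25 and 40 − 12 = 28. With the cap of about 26 weeks, that is 25 to 26 weeks, or nearly all of participation.

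These are durations, not risks. They show only that the wording fails for a substantial part of the study rather than in a rare corner.

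**3. When must a nurse contact the team within 24 hours?**
- 17.5: two triggers, an emergency with the provider unavailable or a concern about the intervention material. The text does not say that these are the only cases.
- 18.2: SAEs within 24 hours. The sentence sets no condition on provider availability or on relation to the material. It names neither the reporter nor the recipient.

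Test case: a participant is admitted to hospital with preeclampsia, her provider is reachable, and nobody questions the intervention material. Neither 17.5 trigger is met, so 17.5 alone does not call for 24-hour contact. If the admission is recorded as an adverse event, it is serious on the hospitalisation criterion in the 18.1 table, and 18.2 requires a report within 24 hours. Following both sections gives the right result; following 17.5 alone does not. The 17.5 triggers are not a strict subset of the SAE rule either, because a concern about the material need not be serious.

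**The case against.** The strongest reply is that the SAE rule is already in the protocol. Section 18.2 is unconditional on its face and provides email or phone for urgent matters. Section 5.2.1 makes the nurses study personnel, so a rule written in the passive voice can reasonably be read to bind them. Section 17.5 nowhere says that its triggers are exclusive. This stands. A reader might infer that the two sections contradict each other, or that maternal SAEs will reach the team late. The documents support neither: a nurse can comply with both, and the 24-hour limit applies throughout.

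A reader might also infer that an exercise injury has no route to the team at all. That goes too far. Section 10.0 describes physical activity as part of the intervention, so such an injury may well come under the second 17.5 trigger, which includes the PIs. What is missing is the mother's own provider as recipient of the clinical concern.

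A further reply is that the reference to the infant is a drafting slip describing NFP habit, and that nurses would call the obstetric provider anyway. They may; NFP's own protocols are not in the documents, so actual misrouting is not shown. Twice-monthly meetings with the home visitors (15.5) and regular site meetings (17.2) also give non-serious concerns a path to the team. None of this makes the written recipient correct. The 17.5 sentence is a stated rule, and for a pregnant participant it cannot be carried out as written.

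**Conclusion.** The recipient in 17.5 is wrong as written: an infant's provider is named for clinical concerns in a study whose participants are pregnant and postpartum women. Before birth that provider does not exist, and only elevated blood pressure has a stated maternal route. The 24-hour wording is a matter of consistency: 17.5 should match 18.2, which already applies.

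This is a minor safety-text correction. No endpoint, analysis or sample size is affected. The documents give no SAE rate for the 20 women, so no number of affected events can be estimated, and no delay is claimed. The week counts depend on the assumed times of birth and entry; the conclusion does not.

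**What to change.** Amend 17.5 as follows.
- Maternal clinical concerns go to the mother's obstetric provider during pregnancy and the puerperium, and to her primary care provider thereafter, as 7.2 already does for blood pressure.
- The infant's primary care provider remains the contact for infant concerns after birth.
- Nurses report every maternal SAE to the study team, including the PIs, within 24 hours of learning of it, whether or not a provider is available and whether or not the intervention material is in question. Add a cross-reference to 18.2.

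Use the same wording in nurse training. The cost is a few lines in a protocol amendment and in the training text, with no new procedures, visits or data. Section 11.2 looks ahead to a larger multi-site trial, so correcting the text now also keeps the error from being carried forward.
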